they were taught they are actually treating patients by stimulating ear acupoints and that the aim of the study was to compare the efficacy and safety of acupuncture administered by an experienced acupuncturist as compared to acupressure administered by unexperienced medical staff after a short training. Patients were told they are receiving ear-point stimulation. Therefore, this study arm was double blinded. SOC was administered as well as described earlier.

Outcomes:

The primary outcome was dyspnea intensity pre- and post-treatment in the 4 days of follow-up. It was measured daily, before and one hour after treatment (for acupuncture and sham-control groups) or after first evaluation (for SOC-control group), via the modified Borg (mBorg) scale, which is a validated scale that has been used to evaluate the degree of dyspnea (0- no dyspnea, to 10- worse dyspnea) in both stable COPD and AECOPD.^{21,22} Dyspnea intensity was chosen as primary outcome since it has been shown to predict clinical outcomes in AECOPD.²³

Secondary outcomes included:

Variation of clinical symptoms: Including cough intensity and sputum production associated with the AECOPD, as evaluated on a Visual Assessment Scale from 0 (no symptom) to 10 (maximally symptomatic), throughout the 4 days of evaluation.

Variation of physiologic features: Venous blood gases (pH and pCO₂) and oxygen saturation were measured before intervention and daily in the four evaluation days. Respiratory rate (RR) was measured daily, before and one hour after treatment (for true acupuncture and sham-control groups) or after first evaluation (for SOC-control group).

Treatment failure: Defined as death during hospitalization or need for noninvasive or mechanical ventilation. Treatment failure incidence was evaluated and compared between the three groups.

Duration of hospitalization: Evaluated and compared between the three study arms.

Safety: Acupuncture-related side effects were systematically evaluated after treatment in the true acupuncture group via the validated Acup-AE questionnaire administered to the patient by the acupuncturist immediately after therapy.²⁴

Minimal sample size: In a previous study evaluating the efficacy of acupuncture vs sham-acupuncture in 68 patients with chronic COPD (34 patients in each group), a 3.6±1.9 units improvement in dyspnea (according to mBorg scale) was found in the acupuncture arm, as

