Statistical analysis: Demographic and clinical data was analyzed at baseline to measure the balance among the study groups. Quantitative variables were described using mean \pm standard deviation or median and 25th-75th percentiles (Q1, Q3) depending on their distribution. Qualitative variables were described using frequency and percentage distributions. Next, we showed that our variables distribute equally between the study groups. For comparing normally distributed variables between our study groups, we used the ANOVA test. For comparing variables that do not distribute normally between our study groups, we used the Kruskal-Wallis test with adaptation to pairwise comparison. For comparing qualitative variables between our study groups, we used the independent Chi-square test and Fisher exact test. Bonferroni adjustment was used for multiple comparisons for each independent comparison of true acupuncture vs sham-control, true acupuncture vs SOC-control and sham-control vs SOC-control. Since the variation of dyspnea intensity between day 1 and day 2 had a normal distribution, a multivariate linear regression analysis was performed after collinearity, interaction and confounding analysis, in order to neutralize the effect of the different sociodemographic and medical covariates on the primary outcome in the 3 study arms. The adjusted unstandardized regression coefficients were given with confidence interval (CI), while

a $p < 0.05$ was considered as statistically significant. Data analysis was performed using IBM SPSS version 22 statistics software.

Results:

Baseline patient data: 104 patients were screened for eligibility from November 2017 to February 2020. Among them, 72 met inclusion criteria and were recruited. Twenty-six of them were assigned to the true acupuncture arm, 24 to the sham-control arm, and 22 to the SOC-control arm. Baseline demographic and clinical characteristics were similar in patients from the 3 study arms as shown in Table 1. To note, all the patients randomized to any of the three groups completed treatments per-protocol (Fig. 1).

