Primary outcome: Baseline dyspnea was similar in the three groups. A statistically significant difference between the three groups in dyspnea intensity was found from the first day of evaluation after treatment (median [Q1, Q3] mBorg score 5.0 [4.0, 5.0] in true acupuncture, 6.0 [4.25, 7.875] in sham-control and 7.5 [5.5, 8.0] in SOC-control, $p=0.014$ – significant difference of both true acupuncture vs sham-control: $p=0.031$, and true acupuncture vs SOC-control: $p=0.014$, but non-significant between sham-control and SOC-control: $p=0.34$), and until day 3 after treatment (Fig. 2A). After adjustment for such covariates in a multivariate linear regression analysis, the association of study arm with improvement of dyspnea from day 1 to day 2 remained statistically significant (Table 2).

Secondary outcomes:

- Patient-reported outcomes:

Baseline VAS scores for cough and sputum intensity were similar in the three study arms (Table 1). No statistically significant difference in the cough intensity was observed between the three study arms throughout the 4 days of follow-up (Fig. 2). However, a statistically lower level of sputum production was observed in the true acupuncture arm as compared with sham-control and SOC-control from day 2 ($p=0.04$) (Fig. 2). Post-hoc analysis showed a statistically significant difference between true acupuncture and sham-control in day 2 ($p=0.024$), day 3 ($p=0.010$) and day 4 ($p=0.018$), while only on day 2 between true acupuncture and SOC-control ($p=0.044$), and no statistically significance between sham-control and SOC-control.

- Physiologic assessment:

Baseline physiologic data were similar in the three groups (Table 1). A statistically significant difference was observed in respiratory rate (RR) at day 2 after treatment ($p=0.002$), with significant difference both between true acupuncture and sham-control ($p=0.005$) and between true acupuncture and SOC-control ($p=0.003$), but not between sham-control and SOC-control

($p=0.050$), while all other RR measurements were statistically similar between the 3 arms throughout the 4-day follow-up (Fig. 3A).

Concerning pH, a statistically significant difference was observed at day 4 between the 3 groups ($p=0.048$), although post-hoc analysis did not show any statistical significance when comparing groups head-to-head (Fig. 3C).

No statistically significant difference was observed when comparing other physiologic measures between the 3 study groups (Fig. 3).

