Dyspnea (mBorg)	8.0 [5.5, 8.75]	6.5 [5.0, 8.5]	7.75 [6.0, 8.5]	0.82
Cough (VAS)	7.5 [5.0, 8.0]	5.0 [5.0, 7.4]	5.0 [3.6, 7.5]	0.35
Sputum (VAS)	6.0 [1.5, 7.5]	6.0 [4.25, 6.0]	5.0 [1.9, 6.0]	0.22
O₂ saturation				
≤ 80%	4 (15%)	1 (4%)	0	0.30
81-89%	9 (35%)	10 (42%)	10 (45%)	
≥ 90%	13 (50%)	13 (54%)	12 (55%)	
PCO₂ (mmHg)				
< 45	6 (23%)	3 (12%)	8 (36%)	
45-60	12 (46%)	17 (71%)	9 (41%)	0.10
60-80	5 (19%)	4 (17%)	5 (23%)	
> 80	3 (12%)	0	0	
pH				
< 7.2	0	0	0	
7.2-7.3	5 (19%)	4 (17%)	1 (5%)	0.30
> 7.3	21 (81%)	20 (83%)	21 (95%)	
Respiratory rate (/min) (median [Q1, Q3])	21 [16, 23.75]	22 [16.5, 26]	20 [16, 22]	0.26

Legend: CCI: Charlson Comorbidity Index; mPAP: Mean Pulmonary Arterial Pressure; SOC: Standard-Of-Care.

Table 2: Multivariate linear regression analysis on variation of dyspnea from day 1 to day 2

Factors and covariates	Adjusted unstandardized coefficient (B)	95% Confidence interval		p value
		Inferior	Superior	
Constant (Intercept)	2.088	-3.409	7.584	0.457
Study Arm				
True acupuncture	2.172	0.421	3.923	0.015
Sham-control	0.390	-1.319	2.099	0.655
SOC-control	0	-	-	-
Cardiovascular comorbidities (0=No, 1=Yes)	-0.322	-2.935	1.391	0.713
Gastroenterological comorbidities (0=No, 1=Yes)	4.703	2.527	6.879	<0.001
Hospitalizations for COPD in the last year	-0.379	-0.756	-0.003	0.048
Age	-0.040	-0.133	0.053	0.400
APACHE-II	0.118	-0.099	0.336	0.287
Charlson Comorbidity Index	-0.026	-0.406	0.354	0.894

Figure 1: Flow-chart

Legend: SOC: Standard-of-care.

Figure 2: Between-group comparison of patient-reported outcomes

[figure not shown]

Figure 3: Between-group comparison of physiologic features

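### No dyspnea analysis adjusts for the pre-treatment day-1 mBorg score that the trial collected; the cost is precision, and no reported conclusion is shown to change

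*Combined protocol and SAP*

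**What the plan says.** Under Outcomes, the primary outcome is dyspnea on the 0 to 10 mBorg scale over four days. There were two readings a day: "It was measured daily, before and one hour after treatment (for acupuncture and sham-control groups"), with the SOC-control arm read at and after a first evaluation. A pre-treatment day-1 score therefore exists, and Table 1 reports it as median [Q1, Q3]: 8.0 [5.5, 8.75] for acupuncture, 6.5 [5.0, 8.5] for sham and 7.75 [6.0, 8.5] for SOC, with p=0.82.

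Dyspnea is then analysed in two ways.

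- **Each occasion separately**, by ANOVA or Kruskal-Wallis, neither with a covariate. Under Results, Primary outcome, the day-1 post-treatment scores are "5.0 [4.0, 5.0] in true acupuncture, 6.0 [4.25, 7.875] in sham-control and 7.5 [5.5, 8.0] in SOC-control".
- **One adjusted model.** The Statistical analysis section reasons that "the variation of dyspnea intensity between day 1 and day 2 had a normal distribution" and states that "a multivariate linear regression analysis was performed after collinearity, interaction and confounding analysis", with the purpose given as "in order to neutralize the effect of the different sociodemographic and medical covariates on the primary outcome in the 3 study arms". The candidate covariates for that screening are not listed. Table 2 has study arm, cardiovascular and gastroenterological comorbidity, COPD hospitalizations in the last year, age, APACHE-II and Charlson index.

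Baseline mBorg is not in Table 2. Its title, "Table 2: Multivariate linear regression analysis on variation of dyspnea from day 1 to day 2", does not say which of the two daily readings is used on either day, and neither does the text.

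**The concern.** The model is meant to remove the influence of patient characteristics on dyspnea. The starting dyspnea score is an obvious candidate for that purpose: it is the same scale in the same patient, and it costs nothing to include.

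Two things are at stake. One is precision, since with 22 to 26 patients per arm a wider interval matters. The other is how a chance baseline difference carries into each analysis. Sham started somewhat lower than acupuncture, so a change from the pre-treatment score leans one way and a raw follow-up comparison leans the other. Acupuncture against sham is the contrast most exposed to this. Results, Primary outcome, tests it unadjusted, and Table 2 prints no adjusted estimate or interval for it.

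**Working it through.** **1. Reproduce the Table 2 figure.** Acupuncture-SOC is 2.172, 95% CI 0.421 to 3.923. The half-width is (3.923 − 0.421)/2 = 1.751 and SE = 1.751/1.96 = 0.893. Then z = 2.172/0.893 = 2.43 and p = 0.015, as printed.

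**2. Approximate means and SDs.** Mean ≈ (Q1 + median + Q3)/3 and SD ≈ (Q3 − Q1)/1.35, a normal approximation.

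| | Acupuncture (26) | Sham (24) | SOC (22) |
|---|---|---|---|
| Baseline mean | 7.42 | 6.67 | 7.42 |
| Baseline SD | 2.41 | 2.59 | 1.85 |
| Day-1 post-treatment SD | 0.74 | 2.69 | 1.85 |

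The pooled baseline SD is √[(25×2.41² + 23×2.59² + 21×1.85²)/69] ≈ 2.32.

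**3. Gain from adjustment.** With equal variances and correlation r, ANCOVA variance is (1 + r)/2 of the change-score variance and 1 − r² of the raw-score variance.

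**4. What r does Table 2 suggest?** If the change starts pre-treatment and all 26 and 22 patients are analysed, the SE of an unadjusted change-score contrast is 2.32 × √[2(1 − r)] × √(1/26 + 1/22) = 0.672 × √[2(1 − r)].

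- r = 0.3 gives 0.80, r = 0.5 gives 0.67 and r = 0.8 gives 0.43.
- Setting this equal to 0.893 gives r ≈ 0.12. If the other covariates inflate the variance by 1.4 (an assumption), r ≈ 0.37. I take roughly 0.1 to 0.35.
- The inference is rough. With no inflation, a baseline SD of 1.85 would give r = −0.39 and 2.6 would give 0.30. These values all point to low r.

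| r | ANCOVA / change | ANCOVA / raw |
|---|---|---|
| 0.1 | 0.55 | 0.99 |
| 0.35 | 0.68 | 0.88 |

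Using 0.37 instead gives 0.68 and 0.86, so the rounding does not matter.

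**5. The chance baseline gap.** Acupuncture minus sham is 7.42 − 6.67 = 0.75, with SE √(2.41²/26 + 2.59²/24) = 0.71, so about one standard error. For a slope b of follow-up on baseline, a change from the pre-treatment score leans toward acupuncture by (1 − b) × 0.75, and a raw score leans against it by b × 0.75. The slope is not given.

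| Assumed b | Change, toward acupuncture | Raw, against acupuncture |
|---|---|---|
| 0.10 | 0.68 | 0.08 |
| 0.35 | 0.49 | 0.26 |
| 0.60 | 0.30 | 0.45 |

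The acupuncture-sham difference implied by Table 2 is 2.172 − 0.390 = 1.782, so the change-score lean is about 38% (b = 0.10) to 17% (b = 0.60) of it. The document does not test that difference.

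**6. Acupuncture-SOC.** The approximate mean gap is 0. Using the median gap of 0.25 and b = 0.10, the shift is 0.90 × 0.25 = 0.225, leaving 2.172 − 0.225 = 1.947, with p ≈ 0.029 at the same SE.

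**7. Does one slope fit all arms?** The slope in an arm is r × (follow-up SD)/(baseline SD). With the day-1 spreads and r from 0.3 to 0.8, it is 0.09 to 0.25 in acupuncture and 0.31 to 0.83 in sham. A single common slope is therefore doubtful.

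**The case against.** The strongest reply is that nothing reported is overturned. Randomization protects the estimates on average, baseline p is 0.82, and lost precision is usually conservative for results that were already significant. Choosing ANCOVA over a valid change score is good practice rather than correction of an error. Baseline mBorg may also have been screened and dropped. All of that stands, except that screening would not help the reader: no candidates are listed, and the term is absent from the model either way.

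The figures are also approximate. The day-1 test was probably a rank test, so variance ratios for means describe it only loosely. The SD of 0.74 comes from an arm whose median equals its upper quartile. The gain is not guaranteed for every contrast: with the printed day-1 spreads and r = 0.8, the sham-SOC ratio of ANCOVA to change-score variance is 1.04.

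A reader might infer stronger things that the document does not support.

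- *That the baseline gap produced the acupuncture benefit.* It is a chance gap of about one standard error. In the raw day-1 comparison with sham (p=0.031) it works against acupuncture, and acupuncture-SOC barely moves.
- *That adjustment would sharply improve on raw scores.* A variance of 36% of raw needs r = 0.8, which sits poorly with the Table 2 standard error.
- *That one covariate removes the lean entirely.* That needs a common slope, which step 7 puts in doubt.
- *That the change starts after the first session and so omits its effect.* This is possible, since the reading is unnamed, but weakly supported. The approximate acupuncture-SOC gap one hour after the first session is already 7.00 − 4.67 = 2.33. A further 2.17 would put the day-2 gap near 4.5. A pre-treatment start fits more naturally, though this is inference.

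**Conclusion.** The point holds as a loss of precision. The pre-treatment day-1 mBorg was collected and tabulated, and no dyspnea analysis adjusts for it. There is no bias on average, and no reported conclusion is shown to change.

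If the change starts pre-treatment, variances are equal and all patients are analysed, r is probably low. The gain over the change score is then sizeable, and the gain over raw scores small. Overlap with the six existing covariates, APACHE-II among them, would reduce the first. If the change starts post-treatment, the (1 + r)/2 factor does not apply directly.

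The chance acupuncture-sham gap leans the change score toward acupuncture and raw scores against it. Common-slope adjustment reduces this but does not remove it if slopes differ by arm. The textual facts are certain; the sizes are illustrative, because r, the slope and the day-2 spread are not given. This is a recommended improvement, not a fatal flaw.

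**What to change.** Add the pre-treatment day-1 mBorg score as a covariate in the Table 2 model, either as ANCOVA on the day-2 score or as a mixed model over the post-treatment readings. Use standard errors robust to unequal spread by arm. Report the adjusted acupuncture-sham contrast with its interval beside acupuncture-SOC.

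When re-running the model, name the day-1 and day-2 readings and state the number analysed. The latter is worth stating because the sham treatment-failure figure of 1 (4.3%) implies a denominator of 23 (1/23 = 4.3%), whereas 1/24 = 4.2%.

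The cost is one degree of freedom, one added contrast and a sentence of text. No new data are needed.

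### The four day-1 dyspnea p-values do not fit Kruskal-Wallis with pairwise tests, either unadjusted or with the stated Bonferroni adjustment; if 0.031 against sham is unadjusted, the plan's own rule makes it 0.093

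*Combined protocol and SAP*

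**What the plan says.** Statistical analysis says that for variables that are not normally distributed "we used the Kruskal-Wallis test with adaptation to pairwise comparison". It adds that Bonferroni adjustment was applied to the three pairwise contrasts (acupuncture vs sham, acupuncture vs SOC, sham vs SOC), with significance at p < 0.05. It does not say whether the pairwise tests use the joint ranks of all three arms or re-rank each pair.

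Results (Primary outcome) gives the day-1 post-treatment summary as "median [Q1, Q3] mBorg score 5.0 [4.0, 5.0] in true acupuncture, 6.0 [4.25, 7.875] in sham-control and 7.5 [5.5, 8.0] in SOC-control", with an overall p of 0.014. It then reports "significant difference of both true acupuncture vs sham-control: $p=0.031", "true acupuncture vs SOC-control: $p=0.014" and "but non-significant between sham-control and SOC-control: $p=0.34". The text does not say whether these three values are raw or already adjusted, and prints no day-1 denominators. Baseline patient data gives 26, 24 and 22 patients per arm and says that all completed treatment.

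**The concern.** Three pairwise rank tests and the overall test on the same data are tied together. Under joint ranking, two pairwise p-values determine the third. Under separate Mann-Whitney tests, the three U statistics determine the rank sums, and so the overall p. The printed values do not respect either link, and 0.014 appears twice.

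What is at stake is the acupuncture vs sham comparison, the contrast meant to separate needling from a placebo response. Its claimed significance rests on 0.031. Table 2 does not fill the gap: it models the change from day 1 to day 2, uses SOC as the reference, and prints no acupuncture vs sham contrast.

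**Working it through.** **Inputs.** Arm sizes 26 (A, acupuncture), 24 (S, sham) and 22 (C, SOC), N = 72, from Baseline patient data. P-values 0.014 overall, 0.031 (A-S), 0.014 (A-C) and 0.34 (S-C), from Primary outcome. Two-sided tests are assumed, as sidedness is not stated. The printed overall p corresponds to H = -2 ln(0.014) = 8.54 on 2 df.

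| Pair | z if raw | z if already ×3 | √(1/nᵢ + 1/nⱼ) |
|---|---|---|---|
| A-S | 2.157 | 2.564 | 0.2831 |
| A-C | 2.457 | 2.829 | 0.2897 |
| S-C | 0.954 | 1.583 | 0.2952 |

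**1. Joint ranks.** The standardized mean-rank gap is d = z × √(1/nᵢ + 1/nⱼ), and the gaps must add: d(A-C) = d(A-S) + d(S-C).

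- Raw: d(A-S) = 0.611 and d(A-C) = 0.712, so d(S-C) = 0.101, z = 0.101/0.2952 = 0.34, p = 0.73 (0.72 to 0.75 over rounding). The printed value is 0.34. The overall statistic is H = [50(2.157²) + 48(2.457²) + 46(0.343²)]/72 = 7.33, p = 0.026, not 0.014.
- Already Bonferroni-adjusted: d(S-C) = 0.820 - 0.726 = 0.094, z = 0.32, adjusted p = 1.0; H = 9.97, overall p = 0.007.
- Starting instead from 0.031 and 0.34, A-C would have to be 0.002 raw (overall 0.006) or 0.0001 adjusted (overall 0.0002).

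At 26/24/22, no mixture of raw and adjusted values closes the gap.

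**2. Separate Mann-Whitney tests.** U = nᵢnⱼ/2 + z√[nᵢnⱼ(nᵢ + nⱼ + 1)/12], ignoring ties. Raw:

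- U(A-S) = 312 + 2.157 × 51.50 = 423.1
- U(A-C) = 286 + 2.457 × 48.33 = 404.8
- U(S-C) = 264 + 0.954 × 45.48 = 307.4

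Rank sums:

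- A: 351 + (624 - 423.1) + (572 - 404.8) = 719.2
- S: 300 + 423.1 + (528 - 307.4) = 943.7
- C: 253 + 404.8 + 307.4 = 965.1

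They total 2628 = 72 × 73/2, as they must. H = 12/(72 × 73) × Σ(R²/n) - 3 × 73 = 7.80, p = 0.020. With the three values taken as already ×3, the same steps give H = 11.2, p = 0.004.

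A tie-corrected numerical search over half-point scores that match the printed quartiles agrees. With raw values, the overall p was 0.0194 to 0.0207 at 26/24/22 and fell to 0.0158 only with arms as small as 26/16/14. With adjusted values, the largest overall p reached was 0.0045.

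**3. What would reconcile the set.** Two small changes work, both under raw Mann-Whitney: the overall p is really about 0.020, or the raw A-C value is about 0.0077 (H = 8.57, overall p = 0.0138). Both leave 0.031 unadjusted. If 0.031 is Bonferroni-adjusted under joint ranks, at least two other values must be wrong. Keeping A-C at 0.014 gives S-C 1.00 and overall 0.007; keeping the overall p at 0.014 gives A-C 0.044 and S-C 1.00.

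**4. Consequence if raw.** 3 × 0.031 = 0.093 against sham; 3 × 0.014 = 0.042 against SOC; 3 × 0.34 exceeds 1, so 1.0.

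**5. Supporting checks (Secondary outcomes).**

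- Day-2 sputum: raw 0.024 and 0.044 (z = 2.257 and 2.014) under joint ranks give H of about 6.3 and overall p of about 0.04, as printed. Read as adjusted, they would give about 0.012. This also suggests that the printed pairwise values are raw.
- Day-2 respiratory rate: under joint ranks, 0.005 and 0.003 give d = 0.795 and 0.860, a gap of 0.065, z = 0.22 and S-C of about 0.83, not the printed 0.050. Under raw Mann-Whitney, the three values give an overall p of 0.0017 if SOC lies between acupuncture and sham, which agrees with the printed 0.002.

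**The case against.** The strongest reply is that the set is not impossible. In a closed test of three arms, each pair takes the larger of its own p and the overall p. A raw A-C value of about 0.0077 would then be reported as 0.014, which explains why that figure appears twice. Data sets exist that match all four values and the quartiles in this way (for example overall 0.0143, A-S 0.0306, A-C raw 0.0077, S-C 0.342). Closed testing controls the family-wise error, and 0.031 against sham would stand under it. This is sound as far as it goes, so a reader should not infer that no procedure could produce these numbers. But the document states Bonferroni and mentions no closed or step-down test.

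Other parts of the reply also stand. Joint ranking is never named, so the 0.73 applies only if it was used. Under raw Mann-Whitney, the three pairwise values fit one another and the quartiles, and only the overall p is off, with 0.020 and 0.014 both below 0.05. The Mann-Whitney result with ties rests on a search, not a proof; over smaller arms and different tie handling the overall p runs from about 0.016 to 0.021. Denominators may vary, since the 4.3% treatment-failure rate in the sham arm implies 1/23.

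The respiratory-rate set may look like a second proven error, but it is not. Its 0.050 could be a misprint. Duration of hospitalization also prints p = 0.050 beside a statement of no difference, while ANOVA on its means and SDs gives F = 3.96/7.28 = 0.54, p = 0.58. The set also fits raw Mann-Whitney.

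Finally, Statistical analysis says that Bonferroni was used. If 0.031 is already adjusted, the sham claim survives, but the other printed values then fit less well.

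**Conclusion.** The point holds in limited form. The four day-1 values cannot all come from Kruskal-Wallis with pairwise tests that are unadjusted or Bonferroni-adjusted. Under joint ranks at the reported arm sizes this is algebra: S-C is about 0.73 raw or 1.0 adjusted, against 0.34 printed. Under separate Mann-Whitney tests, the overall p is about 0.020 raw (0.016 to 0.021) or about 0.004 adjusted, against 0.014 printed.

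The closest readings leave 0.031 unadjusted, which under the plan's rule becomes 0.093. A reader might conclude that acupuncture did not beat sham. The document does not establish that: it depends on 0.031 being raw, which is the likelier reading but is not shown. What can be said is that the sham claim cannot be relied on until the values are reconciled. Because this is the primary outcome and the conclusion may change, it must be fixed.

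**What to change.** Re-run day-1 post-treatment dyspnea from the data with one named pairwise method, stating whether ranks are joint or per pair and how ties are handled. Print n per arm, the overall p, and raw and Bonferroni-adjusted p for each pair. Check the other pairwise results in the same way, including day-2 respiratory rate and its 0.050. Correct whichever values are wrong. If a closed or step-down procedure was in fact used, say so and disclose it as a departure from the stated Bonferroni method. Claim superiority over sham only if it holds under the stated adjustment.

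The cost is a re-run on existing data and corrected text. The downside is that the sham claim may weaken.
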